Although the data collection phase is presented separately to data analysis for clarity of presentation, it will in practice be inter-twined with data analysis. The focus during the case studies is retrospective rather than longitudinal data collection, with the required data being concurrently collected at two sites at a time within the allotted time. The overall timeline of data collection is therefore sequential, rather than contemporaneous across sites. To provide detailed descriptions of attempts to normalize the FTSUG role and speaking up within their organisational contexts, their relationships with relevant internal and external actors, processes and artefacts will be captured via the following NPT informed data collection methods:

- i) An initial period of non-participant observations will allow familiarisation at each site and help researchers build rapport with FTSUGs and other staff. Researchers will observe certain aspects of the FTSUG role e.g. delivering 'speaking up' training and advice to staff, reviewing concerns with colleagues and other FTSUGs within the organisation, attending meetings internally (e.g. patient safety meetings, Board meetings) and externally to the organization (such as the FTSUG regional network meetings). Descriptive free text field notes will be written by researchers as soon after observation periods as possible, with an intention in the early stages of the study to keep the scope of the notes wide on the basis that what previously seemed insignificant may come to take on new meaning in light of subsequent events.
- ii) Qualitative interviews (up to 20 per case study) will be electronically recorded at each site with FTSUGs (maximum n=5); employees who have raised concerns (maximum n=5); key stakeholders and those responding to concerns (n=5), such as Director of Patient Safety, Chief Executive and Trade Union representatives. Other 'front-line' employees, who may or may not have spoken up, but who have not been in contact with the FTSUG will also be interviewed (n=5), to better understand those who are yet to engage with the FTSUG role.
- iii) Documentary analysis of relevant organisational policies, internal communications, reports/investigations undertaken by FTSUGs and reports prepared for the Trust Board on concerns raised by staff and the organisation's cultures (as recommended by Francis, 2015).

Sensitivity to the demands of the FTSUG role and of the issues surrounding researchers' presence potentially influencing speaking up by employees will be central to our conduct throughout the study. For example, during observations periods the researcher will remove themselves from situations where the FTSUG may be approached in person with a concern, or where the FTSUG or any employee requests the researcher to withdraw (discussed further in ethics section). The main objective during observations will be for the researchers' presence to be unobtrusive and to not alter usual practises in any way.

WP3 Data analysis:

A qualitative data analysis package, NVivo11, will be used to organize and store data ready for analysis. Thematic analysis of qualitative data sources underpinned by methodological rigour will be undertaken, as outlined in WP2. Participants' views will be considered against the range of observational and documentary data collected. NPT will inform each step of the analysis with emerging themes being mapped onto the four

generative mechanisms (capability, capacity, potential and contribution), providing rich understanding of the operational context and implementation of the FTSUG role. Analysis of each case study will be individually undertaken before cross-case triangulation occurs (Yin 2009), where case studies will be aggregated thematically and cross-case similarities and differences drawn out.

WP4: Integration and final analysis of findings, report writing and dissemination events - months 22-27 AJ with co-applicants by JM, DK, MA, RM, DA and RAs x2

It has already been noted that key topics and issues emerging from the data will be analysed with reference to the original NPT informed study objectives. To integrate findings across cases a series of NPT thematic charts will be developed for each case study. Detailed exploration of the charted themes will be undertaken, in order to map and understand the range of views and experiences across each site. Several areas of established research into raising concerns and theory will be invoked as analytic lenses to inform the study data analysis and development of the evaluative framework. We know this literature well and have ourselves contributed substantially. In addition to social sciences research, patient safety, health services management research perspectives and perspectives from PPI team members will contribute to the interpretation of qualitative findings. The analysis will not only feed into the final report, but also (consistent with our view that health services research is only as good as its translation into organisational action) outputs aimed at managers and clinicians in healthcare organisations, as detailed below.

Dissemination and projected outputs

Outputs will focus on service organisation and training. Development will be in close collaboration with the PAG, participating NHS Trusts and national bodies to ensure utility and transferability of materials in different organisational contexts. PPI members will also contribute directly to dissemination; this additional work has been costed adequately. NIHR's principles of good dissemination state that researcher should consider:

Stakeholder engagement

The primary stakeholder audience for this research is the community of FTSUGs and the National Guardian's Office. It is important to engage early with the primary audience, which we have achieved by establishing contact with the National Guardian's Office, a small number of FTSUGs and NHS Improvement. We will also engage with this audience throughout the course of the study, being able to share interim findings at the completion of each work package. Secondary audiences include all NHS employees, including senior hospital managers, trades unions and Board members who are clearly identified in the Francis Review as having a key role to play in helping to normalise a speaking up culture. In addition, we will establish an international profile for our work, drawing on the international work of Public Concern at Work (PAG members) as well as building on our existing contacts with healthcare and other industries globally who have an interest in speak up initiatives. Whether NHS employees feel free to speak up is of obvious relevant and importance to NHS patients and the public, who we will engage with through national groups such as Action Against Medical Accidents (PAG members) and local PI groups. Finally, we will build on our existing engagement with the community of academic in the UK and internationally who have an ongoing interest in teaching and researching speaking up by healthcare employees.

Format

A range of tailored outputs will be disseminated to decision makers, patients, researchers, clinicians, and the public at national, regional, and/or local levels as appropriate, including:

- Workshops at the end of the study to deliver findings and recommendations and during the study to allow NHS practitioners to input to the research, gain immediate feedback and support further dissemination.
- Briefing documents and guidance for managers, commissioners and policy makers on findings and implications for future implementation and sustainability of the FTSUG role. Interim briefing documents to be prepared at the completion of each WP.
- Training for FTSUGs and other employees on how to facilitate speaking up which builds on training currently being delivered by Public Concern at Work (PAG members) and Health Education England, using latest video lecture capture technology such as Panopto.
- Masterclasses (via video and online factsheets) for all NHS employees about organisational and interactional techniques for speaking up. Also integrated into undergraduate healthcare curricula and disseminated via Royal Colleges, Trades Unions and professional bodies.
- Accessible public information and ongoing lay summaries about the progress and findings of the research

- and the FTSUG role via a bi-monthly blog/vlog and a dedicated Twitter account.
- Peer reviewed academic journal articles (e.g. BMJ Quality and Safety; Implementation Science) and Health Services professional Journals (HSJ etc.)
- Presentations at NHS conferences attended by managers e.g. NHS Confederation Conference and key academic national and international conferences
- The Final report

Understanding the service context and timing

To ensure that our research reaches public and professionals in healthcare we will fully utilise the networks and network events of Project Advisory Group members, such as Public Concern at Work, the Royal Colleges and Action Against Medical Accidents. In addition, we will build on our ongoing working partnership with the National Guardian’s Office and the FTSUGs Regional Network to ensure direct and timely dissemination of interim and final findings to NHS employees and policy makers. Members of the team will continue to participate in the International Whistleblowing Research Network - with a global membership of over 200 people – where study details and findings will be disseminated as the study progresses.

Plan of investigation and timetable

This section provides a concise summary of the project plan of investigation and a quarterly project timetable showing the scheduling of all key stages in the project, their expected durations, and the timing of key milestones throughout the project including the production of outputs.

- **WP1 (months 1-5):** a systematic narrative synthesis of international literature of ‘Speak Up’ strategies undertaken in healthcare and other sectors.
- **WP2 (months 6-11):** a telephone survey of purposively sampled FTSUGs working in Acute Hospital Trusts and Mental Health Trusts (n=100) which will provide an understanding of how FTSUGs are selected/recruited, deployed and organised and the numbers and types of concerns raised. National stakeholders in the FTSUG process will also be interviewed (n=10), e.g. designers of the system, those regulating and monitoring it, and those able to discuss how FTSUG roles relate in design and implementation to other monitoring systems.
- **WP3 (months 12-21):** based on the findings of the survey, six case study sites (4 Acute Trusts & 2 Mental Health Trusts) will provide an in-depth examination of how FTSUG roles are variously implemented and normalized alongside other local and national roles and initiatives related to developing open reporting cultures in the NHS.
- **WP4 (months 22-27):** integration and final analysis of findings and report writing.
- **Outputs and dissemination events:** publications, workshops, awareness raising and briefings are scheduled throughout the duration of the project

Project Stages & Milestones	Quarterly timeline								
	1-3	4-6	7-9	10-12	13-15	16-18	19-21	22-24	25-27
WP1 Months 1-5 (5 months) Narrative review and synthesis	x	x							
Research ethics and R&D approvals	x	x		x (R&D)	x (R&D)	x (R&D)			
Develop & pilot telephone survey	x	x							
WP2 Months 6-11 (6 months) Telephone survey; sampling and additional R&D approvals for case studies		x	x	x					
WP3 Months 12-21 (10 months) Undertake 6 case studies & consolidation of cases				x	x	x	x		
WP4 Months 22-27 (6 months) Integration of findings, complete analysis								x	x
Project Advisory Group meetings		x		x		x		x	
Outputs: Workshops, publications & other dissemination material/events, blog		x		x	x	x	x	x	x
Outputs: Develop training materials drafting of final report								x	x
Outputs: Progress reports to NIHR				x		x		x	

Table 2 Project timetable

Patient and Public Involvement (PPI)

A group of four PPI members participated in two group discussions of the outline and full application during which they offered constructive direction in the research focus and design of the project and have confirmed the viability and appropriateness of the study. Two of the group will continue contributing directly to the study via the PAG and other research activities listed below. From past experiences, the following are examples of how we anticipate their continued involvement will benefit our research and outputs:

- Ensuring our research processes are in tune with the needs of patients and carers Helping us not lose sight of why the research is important and how the research might positively influence practises from a PPI perspective.
- Contributing to preparation for data collection and data analysis activities, such as reviewing emerging findings and development of later findings through regular discussions with the research team.
- Informing the refinement and accessibility of dissemination materials and participate in workshops and other dissemination events and activities such as authoring blog/vlog content and providing a PPI perspective to training materials for NHS employees, Board members etc.
- Playing a significant role in setting future research priorities.

REFERENCES

- Adelman, K., 2012. Promoting employee voice and upward communication in healthcare: the CEO's influence. *J. Healthc. Manag. Am. Coll. Healthc. Exec.* 57, 133-47-148.
- Attree, M., 2007. Factors influencing nurses' decisions to raise concerns about care quality. *J. Nurs. Manag.* 15, 392-402. doi:10.1111/j.1365-2834.2007.00679.x
- Beckstead, J.W., 2005. Reporting peer wrongdoing in the healthcare profession: the role of incompetence and substance abuse information. *Int. J. Nurs. Stud.* 42, 325-331. doi:10.1016/j.ijnurstu.2004.07.003
- Black, L., 2011. Tragedy into policy: a quantitative study of nurses' attitudes toward patient advocacy activities. *Am. J. Nurs.* 111, 26-35-37. doi:10.1097/01.NAJ.0000398537.06542.c0
- Crossman, R., 1973. *The Diaries of a Cabinet Minister, Vol. 3.* Hamish Hamilton and Jonathan Cape, London.

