The aim of this study is to better understand the introduction of an innovative new role designed to support staff who wish to raise concerns about the quality of patient care. These roles are called 'Local Freedom to Speak Up Guardians' (referred to here as 'FTSUGs'). We are interested in finding out how FTSUG roles are being introduced and normalised into everyday practice in NHS England and whether FTSUGs are helping NHS staff to speak up about their concerns. The study consists of three separate but interrelated work packages (WP). WP1 comprises a critical synthesis of the national and international research and grey literatures on initiatives which have sought to normalise 'speaking up' in healthcare and other industries. WP2 involves telephone interviews with FTSUGs working in Acute Hospital Trusts and Mental Health Trusts and national stakeholders in the FTSUG process, e.g. designers of the system, those regulating and monitoring it, and those able to discuss how it relates in design and implementation to other monitoring systems. WP3 involves 6 in-depth case studies of the implementation of FTSUGs in these areas. A recognized theoretical framework called Normalisation Process Theory (NPT) will be used to structure data generation, analysis and interpretation. We will analyse the six case study sites separately, before integrating and synthesising the emergent findings across all cases. A project report will then be produced describing similarities and differences in the implementation of the FTSUG role across England and whether and how FTSUGs have normalised speaking up by staff and organisational responsiveness to staff concerns. We will also develop induction and training materials and a 'speak up' guide for managers, clinicians and others with an interest in this area.

Research Questions

1. How are FTSUGs being variously deployed, managed and held accountable for their work?
2. How is the work of FTSUGs defined and negotiated in relation to the work of others who also deal with employee concerns and patient safety at local and national levels?
3. Do different implementation models for the FTSUG role impact on the 'freedom to speak up', both in the ways that employees raise concerns and how these concerns are responded to?

Research Aims

- a) To map varying approaches to implementing and configuring FTSUG roles in Acute Trusts and Mental Health Trusts.

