WP2: Survey of FTSUGs and national stakeholders via semi-structured telephone interviews – months 6-11; AJ lead with coapplicants DK, JM, MA, RAsx2

This work package will provide a better understanding of what FTSUGs do within their organisations, by undertaking semi-structured telephone interviews with FTSUGs operating in Acute Trusts and Mental Health Trusts in England (n= 100) and national stakeholders (n=10) in the FTSUG process, e.g. designers of the system, those regulating and monitoring it, and those able to discuss how it relates in design and implementation to other monitoring systems, which will address the following research aims and objectives:

Aim a) To map varying approaches to implementing and configuring FTSUG roles across NHS England.

Aim b) To generate evidence of the extent to which the FTSUG role has been 'normalized' in organisations.

Objective 1. IMPLEMENTATION & USE: Assess the scale and scope of the deployment and work of FTSUGs in NHS England.

Objective 2. IMPLEMENTATION & GOVERNANCE: Assess how the work of FTSUGs is organised and operationalised alongside other relevant local and national roles with responsibilities for managing concerns.

Objective 3. EFFECTIVENESS: Evaluate the comparative effectiveness of different types of FTSUG roles in supporting 'freedom to speak up'.

Following feedback on the outline proposal from the HS&DR panel, we have chosen to undertake WP2 and WP3 with Acute Trusts and Mental Health Trusts. As care delivery organisations, Acute Trusts and Mental Health Trusts face comparable contextual and clinical factors when implementing the FTSUG role. In addition, these Trusts are collectively the most widespread care delivery organisations in England and, since October 2016 at the latest, have at least one FTSUG in post. The FTSUG role is also currently operational in Clinical Commissioning Groups (CCGs), Ambulance Trusts, GP practices and community providers. However, FTSUG implementation is variable, very recent or absent in these organisations, where there are also obvious operational differences to Acute and Mental Health Trusts which would make meaningful comparisons of the FTSUG role difficult to achieve.

WP2 Data collection during months 6 to 9: 110 interviews over 4 months (100 interviews with FTSUGs and 10 interviews with stakeholders, such as regulators, monitors and policy makers).

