- **Respondent demographics:** Location and role within the organisation. Age, gender, ethnicity, years of service, previous posts, training/education.
- **Organisational descriptors:** Organisation size, type, structure and academic status.
- **Organisational structure, process and policy relating to speaking up:**
 - Organisational structures and processes in place for employees to speak up and for hearing and responding to employee concerns.
 - Divisional structures, units and roles assigned with responsibility for responding to concerns.
 - Overview of actions taken in response to concerns, timescale for response.
 - New structures/processes/policies created by FTSUG and resources available to the FTSUG.
- **Evaluation of the local response and commitment to/normalising the FTSUG role:**
 - Examples of barriers/enablers to operationalizing the role and effective response to concerns.
 - Numbers, types and severity of concerns raised since FTSUG post created.
 - Degree to which speaking up activities have led to sustained local positive action.
 - Comparison of intended to actual outcomes/changes resulting from implementation of the role
 - Self-evaluation of the organisational culture and response to implementation of the FTSUG role.

Relevant Key Findings (KFs – see box 1) from the NHS National Staff Survey 2017 will be analysed to further understand some of the institutional characteristics within which FTSUGs work. NHS Staff Survey data

collection occurs annually between September and October, at which time all the FTSUGs in the relevant Trusts will have been in post for at least 12 months. KFs will be published in March 2018, thus available for use in WP2 starting August 2018. Significant differences (as defined and reported within the survey) in KFs between 2015, 2016 and 2017 for each organisation will be collected and analysed.

Box 1: Examples of key finding (KF) from the NHS National Staff Survey

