KF 6 Percentage of staff reporting good communication between senior management and staff; **KF 28** Percentage of staff witnessing potentially harmful errors, near misses or incidents in last month; **KF 24** Percentage of staff reporting most recent experience of physical violence in last 12 months; **KF 27** Percentage of staff reporting most recent experience of harassment, bullying or abuse in last 12 months; **KF 29**. Percentage of staff reporting errors, near misses or incidents witnessed in the last month; **KF 30**. Fairness and effectiveness of procedures for reporting errors, near misses and incidents; **KF 31**.

Publicly available sections of Care Quality Commission (CQC) inspection reports from 2016 onwards will also be collected. For example, the 'responsive', 'safe' and 'effective' sections of the inspection reports will be collected and analysed for evidence of how institutions deal with employee concerns. Importantly, the information from the staff survey and CQC inspection reports will be used to describe the contexts within which FTSUGs operate, rather than drawing direct causal relationships between the staff survey, inspection reports and the extent to which FTSUGs and a speaking up culture have been normalised. However, the total dataset collected in WP2 will be combined to provide a rich and thick description of similarities and differences in FTSUG role implementation, alongside institutional level descriptors of culture, context and speaking up activities by employees, enabling preliminary conclusions to be reached about FTSUGs work and how, when and how often staff concerns are raised.

WP2 Sampling

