Objective 2. IMPLEMENTATION & GOVERNANCE: Assess how the work of FTSUGs is organised and operationalised alongside other relevant local and national roles with responsibilities for managing concerns.

Objective 3. EFFECTIVENESS: Evaluate the comparative effectiveness of different types of FTSUG roles in supporting 'freedom to speak up'.

Objective 4. BARRIERS & FACILITATORS: Identify barriers, facilitators and unintended consequences associated with the implementation of FTSUG role.

Research question 1. How are FTSUGs being variously deployed, managed and held accountable for their work?

Research question 2. How is the work of FTSUGs defined and negotiated in relation to the work of others who also deal with employee concerns and patient safety at local and national levels?

Research question 3. Do different implementation models for the FTSUG role impact on the 'freedom to speak up', both in the ways that employees raise concerns and how these concerns are responded to?

Qualitative case studies can provide rich detailed data, and are particularly useful when trying to understand and compare the implementation of complex interventions in real life settings (such as workplaces) in which the process cannot be controlled. We see the introduction of FTSUG roles as a 'complex intervention' because the normalisation, or otherwise, of the role and the development of a speaking up culture within an organisation depends on the actions of individuals across a range of different contexts which are dynamic, and where competing demands exist within the system. A qualitative approach consisting of observations, documents and in-depth interviews is therefore required to capture and make sense of this complexity. We have designed the study to have extensive input from stakeholder groups at each of the participating organisations to ensure fieldwork proceeds smoothly and that findings and recommendations reflects stakeholder needs.

WP3 Settings/context and sampling

A total of 6 case studies will be identified from the analysis of the data collected in WP2. Taking into account that there are 152 Acute Trusts and 54 Mental Health Trusts, we will purposefully sample 4 Acute Trusts and 2 Mental Health Trusts for this phase of the study. The Project Advisory Group (PAG) will also be consulted about selection of sites to ensure information rich cases which best address the research aims and objectives. Potential perspectives to consider when selecting sites include:

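### Objective 3 and Research Question 3 promise comparative effectiveness and impact of FTSUG role models, which the WP2 and WP3 designs cannot establish

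*Protocol*

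**What the plan says.** Objective 3 appears three times in the Protocol with the same wording: in the general list of Research Objectives, under WP2 and under WP3. It is headed EFFECTIVENESS and is to "Evaluate the comparative effectiveness of different types of FTSUG roles in supporting" the freedom to speak up. Research Question 3, in the general list and again under WP3, asks: "Do different implementation models for the FTSUG role impact on the 'freedom to speak up', both in the ways that employees raise concerns" and how those concerns are answered. Aim c, assigned to WP3 but not to WP2, is more modest: it seeks insights into the benefits and drawbacks of the models.

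The sources offered to meet these goals are:

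- **WP2 interviews** with 100 FTSUGs and 10 national stakeholders. The candidate items include numbers, types and severity of concerns, sustained local action, intended against actual outcomes, and "Self-evaluation of the organisational culture and response to implementation of the FTSUG role". FTSUGs are also asked whether they see their role and speaking up as normalised.
- **WP2 external data.** Significant differences in staff survey Key Findings (KFs) between 2015, 2016 and 2017 are collected and analysed for each organisation, and CQC reports are collected from 2016. These data "will be used to describe the contexts within which FTSUGs operate, rather than drawing direct causal relationships between the staff survey, inspection reports" and the degree of normalisation.
- **WP3**: six purposively sampled Trusts (4 Acute, 2 Mental Health). On timing, "The focus during the case studies is retrospective rather than longitudinal data collection".

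**The concern.** Comparative effectiveness is a claim about what a role model does to speaking up, relative to another model. It needs an outcome that does not depend on who holds the role, and some way of separating the model from the Trust that adopted it. The Protocol names neither in WP2 or WP3. It also withdraws its external Trust-level data from causal use, in the work package that carries Objective 3 without the softer Aim c.

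Two explanations would compete with a model effect. Better-resourced FTSUGs may describe their own work more favourably, and Trusts that fund more time may already have had a better culture. The dissemination section (Format) plans interim briefings at the end of each work package, and guidance for managers, commissioners and policy makers on future implementation. A conclusion on effectiveness drawn from WP2 could therefore circulate before WP3 reports.

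**Working it through.** This is a mismatch between objective and design, so most of the check sets sections side by side. No significance level, power, effect size or standard deviation is stated in the Protocol, so there is no power calculation to reproduce.

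**1. The stated sample (WP2 Sampling).** Read as 10 FTSUGs from each of 10 regional networks: 10 × 10 = 100 FTSUGs. Adding 10 stakeholders gives 100 + 10 = 110 interviews, as stated. The number follows from recruitment, not from a comparison of models.

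**2. Who supplies exposure and outcome in WP2.** Role features (number in post, hours, secondment) and results (concerns, actions, culture, normalisation) both come from the FTSUG in the Trust concerned. The 10 stakeholders are national and speak to the system, not to single Trusts. So in all 100 FTSUG interviews the same informant gives both sides of any cross-tabulation.

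**3. What WP2 does with the data.** WP2 Data analysis plans descriptive statistics, cross-tabulations, scattergrams and thematic analysis. The external Trust-level series is analysed, but as context only.

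**4. What WP3 adds.** Up to 20 interviews per site, of which at most 5 are with FTSUGs. The others are 5 employees who raised concerns, 5 stakeholders or responders, and 5 front-line staff without FTSUG contact: 5 + 5 + 5 = 15. Observation and documents come on top. These sources are independent of the FTSUG, but they are compared thematically, and no outcome is named by which one model would be judged more effective.

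**5. Separating model from context in WP3.** Six sites can split only 1 v 5, 2 v 4 or 3 v 3, so the smaller side has at most 3. WP3 Settings/context and sampling allows sites to be chosen partly on worsening or improving speaking-up indicators, which lie close to the outcome. The theoretical framework section says that the role does not work the same way in every organisation, and that its design will follow local institutional arrangements. That describes confounding of model by context, and no planned step deals with it.

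**6. Scale, for illustration only.** Assume the 100 FTSUGs split by protected time as in the published figures that the Protocol cites (70%, 22%, 8%), with independent responses, two-sided alpha 0.05 and 80% power. The smallest detectable difference in standard deviations is (1.96 + 0.84) × √(1/n₁ + 1/n₂):

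| Contrast | Detectable difference |
|---|---|
| 70 v 22 | 0.68 SD |
| 70 v 8 | 1.05 SD |
| 22 v 8 | 1.16 SD |
| 50 v 50 (best case) | 0.56 SD |

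The point does not rest on these figures. A larger sample would narrow the intervals but would not remove the problems in steps 2 and 5.

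**The case against.** The strongest reply is that this is a declared qualitative study based on Normalisation Process Theory. It plans no effect estimate, and *effectiveness* is meant loosely. The context-only limit on the survey and CQC data is then a safeguard, and the text speaks only of preliminary conclusions and of similarities and differences. Part of this stands: counting sites per side is no criticism of case-study work in itself, and the safeguard is a good one. But Objective 3 is labelled as effectiveness, says comparative, and is kept apart from Objective 4 on barriers and facilitators. If a loose meaning is intended, the wording should carry it.

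Several stronger readings are tempting and are not supported:

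- *That the study has no data independent of FTSUGs.* WP3 has up to 15 other interviews per site, observation and documents, and the Protocol itself notes the limited perspective of FTSUGs and those who engaged with them. The same-informant problem belongs to WP2.
- *That no earlier or comparison series is analysed.* KF differences over 2015 to 2017 are analysed for each Trust, though only to describe context.
- *That WP2 results are only self-ratings.* Numbers of concerns, actions taken and response times are factual in kind, although the FTSUG reports them.
- *That the report will rank models.* No section plans a ranking. It is a risk created by the wording, not a stated intention.

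**Conclusion.** The point holds as a mismatch of wording and design. Objective 3 and Research Question 3 claim a property, a between-model effect on speaking up, that neither work package can deliver. In WP2 all 100 FTSUG interviews share one informant for role type and result. In WP3 six purposive sites leave at most three on the smaller side of any two-way contrast, with context unseparated. WP3 is adequate for Aim c.

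This is something the sponsor should fix, not a flaw that stops the study: no planned data item, sample or procedure has to change, and the modest version of the goal is already in the Protocol. The conclusion rests on the Protocol text alone and does not depend on the assumptions behind the illustrative detectable differences. An unseen analysis plan could add an analysis, but it could not create unconfounded comparison groups.

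**What to change.** 1. Reword Objective 3 in the general list and under WP3 to match Aim c, for example: *explore perceived benefits and drawbacks of different FTSUG models and the mechanisms by which they may support speaking up*. Under WP2, either drop it or limit it to exploratory, FTSUG-reported description.
2. In Research Question 3, in both places, replace *impact on* with *relate to*.
3. State in WP4, and in each interim briefing, that the findings do not establish the relative effectiveness of models.
4. Optional: if a cross-model comparison is shown from WP2, use an outcome that the FTSUG does not supply, namely Trust-level change in KF 29 or KF 30 from 2015 to 2017. Report it as an unadjusted association with a confidence interval, not as an effect. Count each Trust once, since WP2 Sampling allows more than one FTSUG per organisation. Use the published KF values as well as the survey's own significance flags, because flags alone give no interval. KF 31 is left out because its label is missing from the text at hand.

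The cost is a less ambitious stated objective and a few lines of protocol text. Items 1 to 3 need no new data. Item 4 draws on a source that WP2 already uses.
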